## Research Methods

---

Describe ALL the study procedures that human participants will undergo for purposes of the research.

*Keep this in mind - If you are:*

- *Observing participants - describe the setting and what you will document*
- *Asking participants to complete a survey - describe how the survey will be distributed*
- *Interviewing participants - describe how you will interview them and what the setting of the interview will be*
- *Audio or video recording - describe how the audio/video tapes will be used and how confidentiality will be maintained*
- *Conducting secondary analysis - describe the data source and provide a list of the variables that will be obtained and analyzed*

*Include:*

- *Time commitment for each participant including if there are multiple visits (e.g., 30 minutes per week for 3 weeks for a total time of 1.5 hours)*
- *Explain what will happen if the participant no longer wants to participate and they are no longer interested in being in the study. What will happen to data that has already been collected?*
- *Describe what will happen to the data after it is collected and analyzed. If data is presented publicly, will it be identifiable or de-identified?*

\*required

### How will you conduct this study?

*Clearly describe any procedures used during the conduct of the study for each participant population. A step-by-step description is recommended.*

---

A randomized controlled trial with a wait list control will be used in this research. The principal investigator will be involved in every aspect of the research and will train two research assistants to collect data and provide recorded orientation and intervention to participants. To develop orientation and intervention videos, PI will collaborate with [name], who is certified in a variety of mindfulness meditations. [name] will not have any interaction with the participants. She will help the PI design the intervention and record the meditative practice. The PI will record the orientation video in collaboration with [name]. The delivery of these recorded videos to the participants will be done by trained research staff. Some portion of orientation will be in person as well.

First, our community collaborators such as Osher Lifelong Learning Institute (OLLI) and senior

housing apartment will help with advertisement of the study via emailing their members our study flyer. We will also set up a table at these community partners sites for prospective participants to sign up. Once we have enough interested participants (**100 adults**, 50 years and older), we will set up an appointment with them to discuss our study. At this time, our research staff will explain the informed consent and after the potential participants fully consent to understanding the research procedure, its risks and benefits, we will ask them to sign the informed consent, copy of which will be given to them. Unless there is a significant language or cognitive barrier that makes it difficult for the potential participants to answer the questionnaires, no interested older adults will be excluded. Participants' capacity to consent would be determined by asking them if they understood the information about the study and the benefits and risks of participating in the study. The trained research staff will also respond to their questions about participating in the study. The potential participants will be told that they can withdraw from the study at any time if they choose. They will be told that the data they provide will be held confidential and they will not be individually identified or in any way associated with specific responses they supply. This will happen face to face in the participants' apartments in common private spaces such as a computer room or a community room or OLLI classroom, where we can privately talk with participants. We will take approval from the apartment manager and OLLI staff to use such a facility.

Then, participants' baseline data for screening will be collected before randomization. Randomization will be done based on participants race, gender and socio-economic statuses resulting with comparable demographic status in both intervention (n=50) and control group (n=50). Baseline data includes questionnaire on demographic information and measures of loneliness, depressive symptoms, anxiety, self-compassion, and cognitive function (see attached Study questionnaires LKM). The baseline data collection will occur one on one in a common private space in the apartment or OLLI classroom to protect participants privacy and for research staff safety. To further strengthen our staff's safety, they will travel in pairs to collect data and provide intervention. Participants will fill out the questionnaire on their own using either their own smart phone, paper and pen (for which data will be transferred to Qualtrics), or research iPad (however, study ID section will be entered by the research staff and participants are asked to fill out rest of the questionnaire). Our research staff will be there to answer any questions participants may have. We will offer rest/break periods as needed during the data collection sessions. Data will be collected using Qualtrics software, which will be password protected, which will ensure the protection of the participants' data. We may use paper pencil for data collection when needed and transfer the data to Qualtrics. We will destroy the paper data once the data has been cleaned and ready for analysis. The paper questionnaire will have Study ID section same as Qualtrics and personal data will not be collected during baseline or other data collection session. The only time personal information is collected during participants sign up, and this information will be safely locked in PI's office cabinet and will only be used to contact participants for future data collection sessions.

Except for demographic information, other data and some intervention evaluation questions will also be collected at the end of the intervention, at 4 week and 8 week. There will be one extra data collection for control group before they get their intervention at 4 week. If for any reason participants refuse to participate during any part of the study, we will collect the reasons for their premature dropping out of the study. Some of the questions that will be asked to those who drop out of the study prematurely are in "Guide for Quantitative Data Collection" attachment.

The intervention primarily involves orientation and mindfulness practices such as proper posture, breathing techniques. We will also teach them the importance of the intervention and daily

practices, how to deal with thoughts that may arise during the meditation practice, and encourage them to write about their daily meditation experiences in the diary provided to them. We will also teach them loving-kindness meditation and provide them with guided meditation on an MP3 device, which they do not have return upon completion of the study. The orientation and intervention will happen in the lobby area, common space, or OLLI classroom in a group setting. The LKM recording will consist of mindfulness practice where they are guided to focus on compassion and kindness for themselves and others. Recording for both brief orientation and LKM are attached. After intervention session is over, participants are encouraged to practice guided meditation daily using the mp3 device for 20-25 minutes on their own at time appropriate for them. They will be encouraged to write their experience in the diary after the practice, which can take from 5 to 10 minutes daily. The diary will be a small folder with some questions to guide their entries daily. Please see dairy or journal requirement attachment for more information. The diary will be given to the participants after the intervention training. There will be weekly reminders via phone call to practice meditation daily and write their experiences in the diary. Weekly call will be around 5-10 minutes weekly for four weeks.

The orientation is about 10-20 minutes (with both in person and recording) and recorded LKM training is about 30-35 minutes (video links provided under interview section as attachments). We will also have a Questions and Answers session, which could take up 10-20 minutes. Participants will be then given the link to fill out the post intervention questionnaires on their own and if they request paper and pen version, those would be available as well.

After 3 weeks of intervention, we will call to set up an appointment to meet both intervention and control group to collect data for 4 week data collection. At this data collection session, we will also collect 30-day journal folders. At this time, we will also ask for **8-10** volunteers for focus group study (we will have two group of 4-5 participants) and once we have their permission, we will set up another appointment for focus group interview, which may take up to 90 minutes at either OLLI campus or apartment's media room. We will also set up an appointment for control group for their LKM training after collecting time 2 data from them. We will do a month follow-up again at 8 week for intervention group and 4week post-intervention data collection for control group.

There are three areas of outcome measures we are aiming to determine: feasibility, acceptability, and initial efficacy:

(1) feasibility of collecting measures of self-compassion, loneliness, depressive symptoms, anxiety, and cognitive function; (2) acceptability of the intervention (i.e., satisfaction, adherence, recruitment, and retention rates); and (3) initial efficacy (i.e., changes in loneliness along with self-compassion, depressive symptoms, anxiety and cognitive function at immediately post-intervention, at 30 and 60 day follow-up). We will evaluate feasibility through participants' satisfaction, their continued use of intervention after the study completion, how appropriate the intervention was for them, their positive or negative effects associated with the intervention. We will also assess their active and continual participation, retention rates, participation rate, and missing data on collected measures. We will also conduct two focus group with **4-5 participants in each group** at the end of the study to determine the feasibility of the study and how we can further improve the intervention for future research. PI will transcribe the qualitative interviews.

\*required

**What is the anticipated time commitment involved for each study procedure (e.g. 30 minutes for the survey, 1 hour for the interview, etc.)? What is the total time that each participant will spend in the entire study?**

---

*Describe the duration of study participation (i.e. the anticipated amount of time commitment required for each subject), the length and number of study visits, and the timetable for study completion.*

*Describe, in timeline sequence, the activities participants will be asked to perform specifically for the research, and how much time each activity will take. Attach your schedule of assessment, if applicable.*

Each session with participants will take about 30-60 minutes. Please see attached schedule of assessments for a detailed anticipated amount of time commitment.

The total time that each participant will spend in the entire study would be around 300 minutes. The focus group will have additional 90 minutes.

Baseline data collection: 60 minutes

Orientation and intervention and data collection: 60-90 minutes

Post intervention data collection at 4 week: 30 minutes

Time 2 control group data collection: 30 minutes

Follow-up data collection at 8 week: 30 minutes

Daily meditation practice: 20-25 minutes

Daily journal entry: 5-10 minutes.

Weekly call: about 5 -10 minutes

Focus group interview: 90 minutes (2 different groups)

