**Provide the enrollment breakdown number for each participant population**

---

*For example: n= 5 teachers, n = 30 students*

n= 50 intervention, n=50 waitlist control

\*required

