**Include sample size calculations, if applicable.**

Adults age 50 years or older, who are willing to participate will be recruited unless they have a significant cognitive or language barrier that will prevent them from successfully answering the study questionnaires.

We will use a randomized controlled trial (RCT) with waitlist control to determine the intervention's feasibility, acceptability, and initial efficacy. Although the proposed study is a feasibility pilot study, we will investigate the preliminary efficacy of the intervention. Therefore, the sample size for this current pilot study was estimated based on four repeated measurements: (baseline, right after intervention, post-intervention (at one month), and follow-up (at second month). Using an estimated effect size (Cohen's  $f= 0.2$ ), an alpha of 0.05, and a power of 90%, for a repeated measure ANOVA between-within effects, with two groups and four measurement time points, the sample size was determined to be 46. This sample size was then increased by 33% to allow for attrition, to give the total sample of 60. The sample size was determined using G\*Power (v. 3.1.9.7).

**Given the interest from the community, we are increasing our sample size to 100. We do not want to exclude eligible community members who might benefit from participating in the study. This will help increase the study power as well.**

\*required

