**Potential Risks**

---

*Examples of risk include physical risks, psychological risks (such as stress, discomfort, or invasion of privacy) and social risks (such as jeopardy to insurability or employability).*

Describe immediate risks, long-term risks, rationale for the necessity of such risks, alternatives that were or will be considered, and why alternatives may not be feasible.

---

Expected risks to the subject are minimal due to the relaxed nature of the intervention. They may have difficulty practicing meditation at the beginning and some thoughts may arise, but with time, it usually gets better.

They may have discomfort when answering some questions. However, participants can take as many breaks during answering questions as they wish, and they can skip the questions that make them uncomfortable or stop participating in the study.

Describe any potential legal, financial, social, or personal affects on subjects of accidental data disclosure.

---

As we are not collecting any protected health or financial information from the participants, we do not anticipate any personal, financial, social, or legal effects on the subjects. Without having both identifiable documents and study data, there is very minimal chance of data disclosure. Moreover, we are collecting data in Qualtrics, which is always password protected.

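### Allocation is balanced on race, gender and socio-economic status, but no stated analysis includes them; leaving them out can make the efficacy comparison conservative

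*Combined protocol and SAP*

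**What the plan says.** In the combined protocol and SAP, *How will you conduct this study?* describes allocation in one sentence: "Randomization will be done based on participants race, gender and socio-economic statuses resulting with comparable demographic status in both intervention" and control arms. It gives no mechanism (stratified blocks, minimisation or matching), no categories for the factors and no number of strata. The target is "n= 50 intervention, n=50 waitlist control".

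The supplied text has no separate statistical analysis section. The one efficacy test named is in *Include sample size calculations, if applicable*, where the calculation is "for a repeated measure ANOVA between-within effects, with two groups and four measurement time points" and "the sample size was determined to be 46". The same section later says "we are increasing our sample size to 100". No covariate, stratification factor or adjusted model is mentioned anywhere.

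Two other places matter. The hypotheses under *Objectives* refer to the state after 30 days of intervention, and waitlist participants are trained only after their 4-week data have been collected. Week 4 is therefore the visit just before the waitlist arm is trained. Under *Potential Risks*, participants are told "they can skip the questions that make them uncomfortable or stop participating in the study".

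**The concern.** When the arms are made alike on factors related to the outcome, the true sampling variance of the arm difference falls. An analysis that omits those factors still counts their contribution as random error. Its standard error is then larger than the design warrants, its confidence interval too wide, and its test rejects less often than 5% under the null. The trial would pay for balanced allocation and discard the precision it bought.

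How far this applies depends on the comparison made. A comparison of arms at one time point carries the full effect. A group-by-time interaction uses within-person error, from which stable differences between people have already been removed.

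**Working it through.** **Inputs.** From the sample size section: Cohen's f = 0.2, alpha 0.05, power 90%, two groups, m = 4 time points, N = 46, later 100. Not in the documents and therefore assumed: correlation ρ between repeated measures (0.5 unless stated), sphericity, the share R² of variance explained by the three factors, and close balance on them.

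**Step 1: which test gives 46?** For the group-by-time interaction, λ = f²·N·m/(1−ρ) = 0.04 × 46 × 4 / 0.5 = 14.72, with df1 = (2−1)(4−1) = 3 and df2 = (46−2) × 3 = 132. The noncentral F gives power 0.903, so 46 is reproduced. With ρ = 0.3 the answer is 64, and with ρ = 0.7 it is 28. The between-group main effect would need 168 at ρ = 0.5, so it is not the basis of the figure.

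**Step 2: arms compared at one time point, no covariates.** Set the outcome variance to 1. Under balance the arm difference varies in proportion to 1−R², but the unadjusted analysis uses 1.

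- Standard error ratio = 1/√(1−R²)
- Actual alpha = 2[1 − Φ(1.96/√(1−R²))]

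| R² (assumed) | SE ratio | Actual alpha |
|---|---|---|
| 0.05 | 1.026 | 0.044 |
| 0.15 | 1.085 | 0.034 |
| 0.25 | 1.155 | 0.024 |

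Two null simulations with 100 participants gave 0.038 to 0.043, 0.036 to 0.037 and 0.019 to 0.025 without the factors, and 0.039 to 0.053 with them. The direction agrees. The single adjusted value of 0.039 is lower than chance readily explains (simulation standard error √(0.05 × 0.95/4000) = 0.003), so the size is better taken from the formula.

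**Step 3: the same comparison with the baseline score in the model.** Assume a baseline-to-week-4 correlation of 0.5 and the same factor effect at both times.

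- Residual variance with baseline only: 1 − 0.5² = 0.75.
- With the factors as well: (1−R²)[1 − ((0.5−R²)/(1−R²))²] = 0.737, 0.706, 0.667 at R² = 0.05, 0.15, 0.25.
- SE ratio: √(0.75/0.737) = 1.009, √(0.75/0.706) = 1.031, √(0.75/0.667) = 1.061, that is about 1%, 3% and 6%.
- Balance reduces the true variance of the baseline-only estimate to 0.75 − 0.25R² = 0.7375, 0.7125, 0.6875. Actual alpha is 2[1 − Φ(1.96·√(0.75/that value))] = 0.048, 0.044, 0.041.

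**Step 4: the group-by-time interaction.** Null rejection rates from 5,000 simulated trials per row (three binary factors, eight strata, blocks of two, all assumed; simulation standard error about 0.003). The adjusted interaction test lets each factor act on change, which is what factor-by-time terms do.

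| N | Factors explain | Interaction, without / with factors | Group main effect, without / with |
|---|---|---|---|
| 46 | 30% of level, none of change | 0.050 / 0.048 | 0.025 / 0.050 |
| 46 | 10% of change, none of level | 0.038 / 0.051 | 0.049 / 0.050 |
| 100 | 30% of level, none of change | 0.053 / 0.052 | 0.025 / 0.050 |
| 100 | 10% of change, none of level | 0.032 / 0.048 | 0.048 / 0.048 |

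Factors that shift only the level of the score leave the interaction untouched. Factors that predict change make it conservative.

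**Step 5: what adjustment is worth in power.** If the factors explain 5%, 10% or 20% of the variance in change, λ at N = 46 becomes 14.72/(1−R²) = 15.49, 16.36 or 18.40, and power rises from 0.903 to 0.918, 0.932 or 0.958. At N = 100 the interaction already has power of about 0.999 without adjustment (0.987 if ρ = 0.3).

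**The case against.** The strongest reply is that the named test is the interaction, that efficacy is described as change in the scales, and that race, gender and socio-economic status do not vary over eight weeks. Step 4 supports this: for level-only effects there is no conservatism to remove. A reader might infer from the mismatch that the named test's intervals are too wide as a matter of course. The documents do not support that, because it requires the factors to predict change. It is also true that entering the factors as main effects only would not alter the interaction test with complete data, since the person-level term already absorbs them.

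A second reply is that no section names a week-4 test. That is correct, but the hypotheses and the waitlist timing both point to week 4. By week 8 both arms have been trained, and a four-time interaction does not isolate the treated-versus-untreated contrast.

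Third, the test is named only to size the trial, so the plan is not committed to an unadjusted analysis. This also stands. The gap is that the factors used for allocation are not carried into any stated analysis.

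Finally, a reader might infer from the freedom to skip questions that staff will place people with a blank race or income item by judgement. The documents do not say so, and the questionnaire is an attachment not seen here, which may already offer a decline option.

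**Conclusion.** The point holds in a limited form. Allocation is balanced on three factors, the only named efficacy test has just group and time, and omitting the factors can make inference conservative. At a single time point without covariates the standard error is too wide by about 3% to 15% for an assumed R² of 0.05 to 0.25. With the baseline score in the model the figure is about 1% to 6%, under the further assumptions of Step 3. For the interaction the loss is nil unless the factors predict change. All sizes rest on assumed R² values and on allocation achieving close balance.

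Severity is low. The error does not inflate false positives, the trial is a feasibility pilot, and at 100 participants the interaction has ample power under the plan's own effect size. It is worth correcting because the correction is almost free.

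**What to change.** State that the LKM-versus-waitlist comparison of each outcome, in particular at week 4 before the waitlist arm is trained, adjusts for the baseline score and for race, gender and socio-economic status in the categories used for allocation. If the repeated-measures interaction is kept, include factor-by-time terms. Name the allocation method and the categories, so that the analysis can match them.

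Cost: no new data or visits, and a few degrees of freedom out of about 100. If the factors had, say, 3, 2 and 2 levels (an assumption), main effects use 2 + 1 + 1 = 4. The factor-by-time terms use 4 × 3 = 12 of the (100−2) × 3 = 294 within-person error degrees of freedom.

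Optional and minor: give each allocation factor a 'not stated' level, so that anyone who skips the item is still allocated by the scheme.

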#### Describe how subjects will be recruited.

---

We, either the PI or research assistant (CITI-trained), will be recruiting adults aged 50 or older living in Southern Nevada. The research team will recruit 100 older adults from different senior homes or institutions that serve older adults, such as the Osher Lifelong Learning Institute (OLLI) at UNLV, with approximately equal numbers of participants (**n = 50**) in each RCT condition. Senior housing and OLLI staff will help advertise our study to their residents/members by posting flyers or emailing the flyer (they will not be involved in recruitment, data collection, or answering questions; they will direct the potential participants to us for any research-related questions). The research team will also directly work with the onsite manager of the senior apartments to post our flyers, promote our study, and recruit from the sites. Once the research team has received approval from the apartment manager, we will have a table in the lobby to recruit potential participants, we will also post flyers in the lobby area so interested participants can directly call the PI. The PI will ask the apartment complex to provide a facility authorization letter once approval to use the facility is received.

Recruitment will occur face-to-face at the older adult's apartment complex (probably in the lobby area, where we will obtain potential participants' contact information) or via phone (if potential participant call us with interest to participate). We will also use the OLLI site for recruitment, and approval to use the facility will be sought. During the recruitment phase, research team is only collecting potential participants name and contact information for screening visit.

At the end of the intervention, we will also recruit **8-10** volunteers from the study to participate in **two focus groups (each with 4-5 participants)** to further collect qualitative data on the feasibility of the study. During the final data collection at the end of the fourth week research team will ask the participants if they would like participate in a focus group interview. We will randomly choose **8-10** participants from the interested pool of the participants.

Describe the type of documents used (e.g., flyers, email, verbal announcements, etc.).

---

Study flyer will be used to advertise the study. Advertisement emails will be sent to apartment staff and OLLI staff to email it to their residents/members.

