**How will you protect the subjects privacy during research activities?**

---

*Privacy refers to the environment in which data are collected from participants and the individual's interest in controlling the access of others to themselves (e.g., interviewing participants individually in a place where personal responses will not be seen or overheard, collecting only the minimum necessary PII to carry out the research, etc.).*

We will be collecting data and implementing the intervention either at the participant's home or a mutually agreed upon venue. We will make sure the mutually agreed upon venue is private and secure so that the risk of being overheard is zero. After the data collection, the indefinable data will be locked in a briefcase before transferring the paper records to the UNLV secure file cabinet. Since the main study's de-identified data are collected in Qualtrics, the data will be password protected.

We will conduct focus group interviews via phone conference call or in person. After the recording is started, we will ask participants to only use their first names. We will let the participants know that once the recording is transcribed, the audio recording will be destroyed and the transcription will not have any identifiable information. Moreover, pseudo names will be used instead of their real names.

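### Group meditation sessions may be held in the lobby although the plan promises a private venue; waitlist controls may be exposed before week 4, and the visible text describes no safeguard or exposure measure

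*Combined protocol and SAP*

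**What the plan says.** **Venue.** *How will you conduct this study?* states: "The orientation and intervention will happen in the lobby area, common space, or OLLI classroom in a group setting". The same section, where it describes consent, already names closed rooms: a computer room, a community room or an OLLI classroom.

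**Privacy.** *How will you protect the subjects privacy during research activities?* states: "We will be collecting data and implementing the intervention either at the participant's home or a mutually agreed upon venue". It goes on: "We will make sure the mutually agreed upon venue is private and secure so that the risk of being overheard is zero".

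**The lobby.** *Describe how subjects will be recruited* shows that the lobby is an open area: "we will have a table in the lobby to recruit potential participants, we will also post flyers in the lobby area".

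**Who is randomised.** "The research team will recruit 100 older adults from different senior homes or institutions that serve older adults", and "Randomization will be done based on participants race, gender and socio-economic statuses". Site and building are mentioned neither as a stratification factor nor as a unit of allocation.

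**Control timing.** "There will be one extra data collection for control group before they get their intervention at 4 week". Their LKM training is arranged after the Time 2 data are in.

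**What participants take home.** Trained participants keep an MP3 device holding the guided meditation and are asked to practise daily for 20-25 minutes.

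**The concern.** Two things look wrong.

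First, the venue text and the privacy text cannot both be followed. The privacy text names the intervention explicitly, so it cannot be read as applying to questionnaires only.

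Second, week 4 is the last point at which a trained arm is compared with an untrained one. If neighbours or fellow OLLI members are allocated to different arms, a control could overhear or join an open session, or borrow the recording, before giving Time 2 data. Exposure of this kind moves the control mean toward the intervention mean, so the estimated effect is too small. If exposure is not recorded, a small or null week-4 difference could mean either that LKM does little or that the controls had some of it. Estimating preliminary efficacy is a stated aim of this pilot, so a shrunken estimate would carry forward into later work.

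**Working it through.** **1. Venue statements side by side.**

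| Topic | Conduct section | Privacy section |
|---|---|---|
| Place | Lobby, common space or OLLI classroom | Participant's home or an agreed venue |
| Format | Group | Not stated; a home does not fit a group session |
| Standard | None stated | Private, secure, no chance of being overheard |

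Only the OLLI classroom can clearly satisfy both columns. The lobby cannot, and an unspecified common space may not.

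**2. Reproduce the plan's sample size.** Inputs from the sample-size section: f = 0.2, alpha = 0.05, power 90%, k = 2 groups, m = 4 time points, stated N = 46. The plan does not give the correlation among repeated measures (rho) or the nonsphericity correction (epsilon); rho = 0.5 and epsilon = 1 are assumed. For the within-between interaction:

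- lambda = f² × N × m × epsilon / (1 − rho) = 0.04 × 46 × 4 / 0.5 = 14.72
- df1 = (k − 1)(m − 1) = 3; df2 = (N − k)(m − 1) = 132
- power from the noncentral F = 0.903; N = 44 gives 0.888

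N = 46 is reproduced. It depends on rho: 0.3 would give 64, and 0.7 would give 28.

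**3. Model the dilution.** If a share c of the treatment effect also appears in the control arm, the contrast becomes (1 − c) times its true size, and f becomes 0.2 × (1 − c). This covers a fraction c of controls responding fully, or all controls responding by a fraction c. The documents give no value for c, so 10 to 30% is an assumed range.

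Example: c = 0.2, N = 46. f = 0.16; lambda = 0.0256 × 46 × 4 / 0.5 = 9.42; power = 0.719.

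| Analysed | c = 0 | 10% | 20% | 30% |
|---|---|---|---|---|
| 46 | 0.903 | 0.826 | 0.719 | 0.590 |
| 67 | 0.981 | 0.948 | 0.883 | 0.774 |
| 100 | 0.999 | 0.994 | 0.976 | 0.926 |

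The row of 67 is 100 × (1 − 0.33), which treats the plan's 33% attrition allowance as a loss rate. The row of 100 is the current maximum with no loss.

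**4. Baseline to week 4 only.** The four-time-point model includes a time after the controls are trained. With m = 2, and f = 0.2 and rho = 0.5 kept as assumptions, power with 100 analysed is 0.977 with no dilution and 0.946, 0.887 and 0.792 at 10, 20 and 30%.

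**5. Bias.** The expected estimate is (1 − c) times the true effect whatever N is. At c = 0.2, a true difference is reported on average as 80% of its size.

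**The case against.** The strongest reply is that nothing shows exposure will happen. The documents do not say that both arms live in one building, that controls attend or pass sessions, or that OLLI members live at a study site. They recruit from several homes and institutions. This stands: shared sites are a reasonable inference from on-site recruitment and individual randomisation, and no more than that.

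The mechanism is also weaker than the lobby suggests. The group session is a single meeting: 10-20 minutes of orientation, 30-35 minutes of recording and 10-20 minutes of questions. Most of the dose is daily practice with a personal device, supported by a diary and weekly calls. Overhearing one session is not the intervention. A shared recording is at least as likely a route, and a change of room would not close it. This stands too, and is why the fix goes beyond the venue.

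A reader might infer that nobody will record control exposure. The documents do not support that: the questionnaires, the data-collection guide and the schedule of assessments are attachments not seen here. Only the visible text can be said to lack such a measure.

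Finally, 46 is the pre-attrition figure behind the earlier target of 60. The maximum is now 100, where power on the plan's model stays above 90% at 30% dilution. This stands for power; it does not answer the bias. Nor does dilution of this kind threaten the feasibility and acceptability objective.

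**Conclusion.** The venue contradiction is certain and needs reconciling whatever one thinks of exposure. Control exposure is a plausible risk against which the visible text describes no protection. It is not an established fact, and the stronger statement that lobby sessions expose controls and dilute the contrast goes beyond the documents.

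The size depends on an unknown rate. Under assumed dilution of 10 to 30%, the loss of power is serious with 46 analysed (83 to 59%), moderate with 67 (95 to 77%) and small with 100 (99 to 93%). The week-4 contrast alone is more sensitive (95 to 79% with 100 analysed). All of these rest on f = 0.2, rho = 0.5 and epsilon = 1. The shrinkage of the effect estimate does not depend on those values or on N.

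This is worth correcting because the correction is cheap and, without it, a weak week-4 result would be hard to interpret.

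**What to change.** - **Venue.** In *How will you conduct this study?*, replace the lobby and common space with the closed rooms already named there (computer room, community room, OLLI classroom), attended by the allocated arm only. Removing the lobby alone would leave a possibly open common space. Align the privacy section, including its reference to the participant's home, with group sessions in these rooms.
- **Recording.** Ask intervention participants not to share the recording until the controls have been trained.
- **Measurement.** Unless the attached questionnaire already has it, add one item to the controls' Time 2 questionnaire: whether they have attended, heard or practised LKM since baseline. This captures every route of exposure.
- **Analysis.** Keep the as-randomised comparison as the main analysis and report the proportion of controls exposed. Any analysis leaving out exposed controls should be supportive only, with a stated warning that it excludes people after randomisation from one arm, breaks randomisation and may add bias.

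The cost is room booking, one instruction and one extra item at an existing visit.
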